### **2.9.2.2 Calculation of Compliance Rates**

The method used to calculate the compliance rates of QoL assessment (See Tables 35) is calculated as the number of forms received out of the number of forms expected at each assessment point defined based on the following principles:

- 1) At baseline: the number of forms expected is the total number of patients who are eligible for the study and required to fill out QoL questionnaires.
- 2) At 4 weeks , 3 months and 6 months after start of Radiotherapy: the number expected at the cycle is the total number of patients who submitted the baseline QoL form and were alive.

### **2.9.2.3 Cross-sectional analysis**

The mean and standard deviation of QL scores at baseline (table 36) and mean and standard deviation of QoL change scores from baseline at each assessment time will be calculated (see Table 37). Then Wilcoxon Rank-Sum test is used to compare two treatment arms in terms of change in QOL score at each assessment time from baseline (see Table 37).

### **2.9.2.4 QoL Primary analysis**

The primary end point for the QoL analysis is the mean score change (baseline to 3 months after treatment). Two samples t-test will be used to test whether the changes in QoL score was significantly different at 3 months after treatment between two treatment arms.

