## 2.3 Analysis Conventions

All comparisons between treatment arms will be carried out using a two-sided test at an alpha level of 5% unless otherwise specified. No formal adjustments will be made for the multiplicity of inferences for multiple clinical endpoints.

The baseline stratification factors that will be used to adjust the analyses where appropriate are listed below:

- Histology (radioresistant vs. radiosensitive)
- “Mass”\* on imaging (present vs. absent)

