## 2.9.2 Analysis

All patients who have completed a baseline quality of life questionnaire (EORTC QLQ-C30 and QLQ-BM22) and at least one follow-up questionnaire are included quality of life analysis.

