### 2.9.2.1 Determination of Assessment Times

The following will be the scheme to determining the time frame of a QoL assessment:

- 1) Baseline: Baseline evaluation is the QoL questionnaire collected closest, but no more than 7 days prior to, the date of randomization;
- 2) At week 4 after start of Radiotherapy: If the QoL is assessed within 2 weeks before or after the week 4 after start of Radiotherapy was given.
- 3) At 3 months after start of Radiotherapy: If the QoL is assessed within 4 weeks before or after the 3 months evaluation.
- 4) At 6 months after start of Radiotherapy: If the QoL is assessed within 4 weeks before or after the 6 months evaluation.

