### **2.9.2.5 QoL response analysis**

QOL response analysis is the CCTG QoL committee recommended analysis, and is calculated as follows: for a functional domain, a change score of 10 points from baseline was defined as clinically relevant. Patients were considered improved if reported a score 10-points or better than baseline at any time of QOL assessment. Conversely, patients were considered worsened if reported a score minus 10-points or worse than baseline at any time of QOL assessment without above defined 10-point improvement. Patients whose scores were between 10-point changes from baseline at every QOL assessment were considered as stable. In contrast to functional domains, for the determination of patient's QOL response, classification of patients into improved and worsened categories is reversed for symptom domains and single items. Chi-square and Mantel-Haenszel chi-square test for trend is used to test if there is a trend that patients in one treatment arm have higher proportions in the better QoL categories than those on the other arm. (Table 38).

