**Table 37: Mean QOL change scores from baseline for global domain at each assessment time**

Assessment	SBRT		CRT		P value*
	N	Mean (SD)	N	Mean (SD)	
At 4 weeks	***	*** (**)**	***	*** (**)**	0.**
At 3 Months	***	*** (**)**	***	*** (**)**	0.**
At 6 Months	***	*** (**)**	***	*** (**)**	0.**

\*Wilcoxon test.

(There will be one table for each domain/item).

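### The primary QoL test is an unadjusted t-test on change: valid, but generally less precise than ANCOVA on the baseline score already collected, and missing from Table 37

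*SAP*

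**What the plan says.** SAP 2.9.2.4 makes the mean change from baseline to 3 months the primary QoL endpoint and specifies the test: "Two samples t-test will be used to test whether the changes in QoL score was significantly different at 3 months after treatment". It names no covariate and cites no table.

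SAP 2.9.2.3 tests the same change scores another way: "Wilcoxon Rank-Sum test is used to compare two treatment arms in terms of change in QOL score at each assessment time from baseline". That result goes to Table 37, headed "Mean QOL change scores from baseline for global domain at each assessment time" and repeated for each domain or item. The shell has N and mean (SD) per arm at 4 weeks, 3 months and 6 months, and one p-value column, footnoted as Wilcoxon.

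On the data available, SAP 2.9.2 says: "All patients who have completed a baseline quality of life questionnaire (EORTC QLQ-C30 and QLQ-BM22) and at least one follow-up questionnaire are included" in the QoL analysis. SAP 2.9.2.1 fixes the baseline: "Baseline evaluation is the QoL questionnaire collected closest, but no more than 7 days prior to, the date of randomization".

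On adjustment in general, SAP 2.3 says: "The baseline stratification factors that will be used to adjust the analyses where appropriate are listed below". The list is histology and mass on imaging. The baseline QoL score is not on it. Protocol 14.7 mentions neither the t-test nor any adjustment for baseline.

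**The concern.** There are two separate points.

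First, subtracting the baseline score fixes the slope of the 3-month score on baseline at 1. If the true slope is lower, as it is whenever the correlation is below 1 and the SDs are equal, the change score over-corrects and adds noise. ANCOVA estimates the slope from the data. The baseline score is already in hand, so the precision is given up for no benefit.

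Second, two tests are specified for one 3-month comparison, and only the one not called primary is tabulated. A reader of Table 37 would take the Wilcoxon p-value as the result. No QoL shell shows a difference between arms or a confidence interval.

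The stakes are limited. QoL is a secondary endpoint, and the stated test does not inflate type I error.

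**Working it through.** **Inputs from the documents**

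- Allocation 1:1 (SAP 1.1); two-sided 5% level (SAP 2.3).
- Total 228, with 15% assumed to drop out or be inevaluable for pain response (SAP 1.2). The 228 reproduces from 17% versus 34% at 80% power with a continuity-corrected two-proportion formula, giving 114 per arm.
- 10 points as a clinically relevant change (SAP 2.9.2.5). This is a threshold for change within a patient; here it serves only as a reference size for a difference between arms.

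There is no QoL sample size, power, SD or correlation in the plan to reproduce.

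**Assumptions**

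- The 15% is applied to QoL as well: 228 x 0.85 / 2 = 96.9, taken as 97 per arm.
- Baseline SD 25, with 20 and 30 as the range.
- Correlation r between baseline and 3-month scores from 0.3 to 0.9.
- k = SD at 3 months / SD at baseline, set to 1.0 or 1.2.

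**Variance ratio**

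In units of the baseline variance, the change score has variance 1 + k² − 2rk and the ANCOVA residual has variance k²(1 − r²). The difference is

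(1 + k² − 2rk) − k²(1 − r²) = (1 − rk)²

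This is never negative and is zero only when rk = 1. So the direction of the result does not depend on the assumed values. At k = 1 the ratio of ANCOVA to change-score variance simplifies to (1 + r)/2.

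| r | Ratio, k = 1.0 | SE smaller by | Ratio, k = 1.2 | SE smaller by |
|---|---|---|---|---|
| 0.3 | 0.65 | 19% | 0.76 | 13% |
| 0.5 | 0.75 | 13% | 0.87 | 7% |
| 0.7 | 0.85 | 8% | 0.97 | 2% |
| 0.9 | 0.95 | 2.5% | 0.98 | 1% |

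**Half-width at SD 25, k = 1, r = 0.5, 97 per arm**

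- Change score: SD = 25 x sqrt(2 x 0.5) = 25; half-width = 1.972 x 25 x sqrt(2/97) = 7.08 points.
- ANCOVA: residual SD = 25 x sqrt(0.75) = 21.65; half-width = 1.972 x 21.65 x sqrt(2/97) = 6.13 points.

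**Power for a 10-point difference (noncentral t, 97 per arm, r = 0.5)**

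| Baseline SD | k | t-test on change | ANCOVA |
|---|---|---|---|
| 20 | 1.0 | 93% | 98% |
| 25 | 1.0 | 79% | 89% |
| 30 | 1.0 | 64% | 76% |
| 25 | 1.2 | 70% | 76% |

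**Simulation check**

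The setting was 4,000 trials, normal data, 97 per arm, SD 25, r = 0.5 and k = 1, with histology and mass in the model but not prognostic. With no true difference, the rejection rate was 0.054 for the t-test and 0.052 for ANCOVA, so both are valid. With a 10-point difference, power was 0.790 (t-test), 0.775 (Wilcoxon) and 0.879 (ANCOVA). The empirical SE ratio was 0.87, against sqrt(0.75) = 0.866 from the formula. The t-test and Wilcoxon reached different verdicts in 5.0% of those trials.

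**Table shells**

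Table 35 is compliance, Table 36 is baseline scores, Table 37 is mean change with the Wilcoxon p-value, and Table 38 is the response categories with chi-square and trend tests. None has a cell for the t-test.

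**The case against.** The strongest reply is that a simpler valid test on a secondary endpoint is a design choice, and that the loss in this trial cannot be known. All of the sizes rest on assumed SDs and correlations. Section 2.9.2.4 names no QoL scale, and both quantities would vary by scale. Protocol 14.7 gives prominence to the improved/stable/worsened analysis, which SAP 2.9.2.5 describes as the group's recommended one. This much stands: the size is conditional and the test is not an error. It does not alter the direction, which follows from the algebra at 1:1 allocation.

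On Table 37, one can say that the shell agrees with 2.9.2.3, which cites it, and that a reader could rebuild the t-test from N, mean and SD. The shells are also not a complete list of outputs: SAP 2.7.1.1 cites a Table 31b that has no shell. So the gap may be partly one of formatting. Even so, an analysis labelled primary should have a planned place in the output, and a reader should not have to reconstruct it.

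On timing, SAP section 1 says that data have been collected and cleaned, and the trial is not blinded. Changing a primary QoL test at that stage therefore needs a dated justification. That adds to the work but does not remove the reason for the change.

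**Conclusion.** Both points hold. The t-test on change is valid but generally less precise than ANCOVA on a baseline score that every analysed patient has. The standard error would be about 2.5% to 19% smaller for r from 0.9 down to 0.3 with equal SDs, and about 1% to 13% smaller with a 3-month SD 1.2 times the baseline SD. These sizes depend on assumed SDs and correlations and, for half-width and power, on the borrowed 15% loss. The direction does not. The Table 37 gap rests on no assumption: its only p-value is not from the test called primary. This is an improvement worth making to a secondary analysis. It is not a threat to the trial's main conclusion.

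**What to change.** In SAP 2.9.2.4, replace the t-test with ANCOVA of the 3-month score on arm, baseline score, histology and mass, using the pre-randomization baseline of 2.9.2.1. In Table 37, add the adjusted difference (SBRT minus CRT), its 95% confidence interval and the ANCOVA p-value at 3 months, marked as primary. Label the Wilcoxon p-value as a sensitivity analysis. If the t-test is kept, Table 37 still needs a column for it. Record the date of and reason for the change, because the data had already been collected.

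The cost is SAP wording, one added block in Table 37 and minor programming. No new data are needed and validity under randomization is kept. The change does not settle which QoL scale is primary, and it does not deal with scores missing through death or dropout.

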10.1.5 Evaluable for Quality of Life Assessment

All patients who have completed a baseline quality of life questionnaire (EORTC QLQ-C30 and QLQ-BM22) and at least one follow-up questionnaire are evaluable for quality of life assessment.

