Assuming a 15% drop out/inevaluable rate, we expect the complete pain response rates for the intent-to-treat analysis to be 17% and 34% for the CRT and SBRT arms, respectively. The sample size for the phase III study is 228. Multiple sensitivity analyses will also be performed to further evaluate the results: (i) complete case analysis that excludes those with missing/inevaluable; (ii) multiple imputation analysis that assigns different portions of those missing/inevaluable to be either responders or non-responders. A secondary “as treated” sensitivity analysis will be performed to include only eligible patients who have received protocol-assigned radiation therapy.

Table: Sample Size Parameters for a Subsequent Randomized Controlled Trial

| CRT response | SBRT response | Effect size | Drop-out rate | Total Sample Size |
|--------------|---------------|-------------|---------------|-------------------|
| 10 | 30 | 20 | 0.1 | 160 |
| 10 | 30 | 20 | 0.05 | 152 |
| 15 | 35 | 20 | 0.1 | 186 |
| 15 | 35 | 20 | 0.05 | 176 |
| 20 | 40 | 20 | 0.1 | 206 |
| 20 | 40 | 20 | 0.05 | 194 |
| 25 | 45 | 20 | 0.1 | 220 |
| 25 | 45 | 20 | 0.05 | 210 |
| 30 | 50 | 20 | 0.1 | 230 |
| 30 | 50 | 20 | 0.05 | 218 |
| 10 | 25 | 15 | 0.1 | 252 |
| 10 | 25 | 15 | 0.05 | 238 |
| 15 | 30 | 15 | 0.1 | 298 |
| 15 | 30 | 15 | 0.05 | 284 |
| 20 | 35 | 15 | 0.1 | 338 |
| 20 | 35 | 15 | 0.05 | 320 |
| 25 | 40 | 15 | 0.1 | 370 |
| 25 | 40 | 15 | 0.05 | 350 |
| 30 | 45 | 15 | 0.1 | 392 |
| 30 | 45 | 15 | 0.05 | 372 |

This table shows potential sample sizes for the planned RCT study with two-sided alpha = 0.05 and power = 80%. The sample size is very sensitive to the CRT response rate. For example, for an effect size of 20%, if the response rate with CRT is 10%, the sample size will be 160 patients while if the response rate is 30%, the sample size will increase to 230.

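### The primary QoL test is an unadjusted complete-case t-test at 3 months and omits some patients in the SAP's own QoL set; a repeated-measures model is a cheap improvement

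*SAP*

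**What the plan says.** SAP 2.9.2.4 defines the endpoint: "The primary end point for the QoL analysis is the mean score change (baseline to 3 months after treatment"). It tests that endpoint as follows: "Two samples t-test will be used to test whether the changes in QoL score was significantly different at 3 months after treatment". No covariate, model or treatment of missing scores is mentioned.

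Who belongs to the QoL analysis is set more widely. SAP 2.9.2 says that patients with a baseline form and "at least one follow-up questionnaire are included quality of life analysis". Protocol 10.1.5 has the same rule: those with a baseline form and "at least one follow-up questionnaire are evaluable for quality of life assessment".

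A form counts as the 3-month form under SAP 2.9.2.1 "If the QoL is assessed within 4 weeks before or after the 3 months evaluation".

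Two other QoL analyses do use the remaining forms. SAP 2.9.2.3 compares change scores at each visit by Wilcoxon test (Table 37). The response analysis in SAP 2.9.2.5 looks across all visits: "Patients were considered improved if reported a score 10-points or better than baseline at any time of QOL assessment".

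For compliance, SAP 2.9.2.2 counts follow-up forms as expected only from living patients: "the number expected at the cycle is the total number of patients who submitted the baseline QoL form and were alive".

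For the primary pain endpoint, by contrast, protocol 14.2 counts missing as non-response, and protocol 14.3 adds complete-case and multiple-imputation sensitivity analyses. Neither document has anything comparable for QoL.

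**The concern.** A patient who completes the baseline and 4-week forms and then dies, deteriorates or stops attending is in the stated QoL set but has no value in the primary QoL test. The plan does not say how that patient counts.

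In patients with metastatic disease, those without a 3-month form are probably sicker than those with one. A completers-only mean would then describe patients well enough to return, and the 3-month change would look too good in each arm. If the extent or pattern of that selection differs between arms, the comparison shifts as well. Because the compliance denominator drops patients who have died, form completion can look high while the scored group shrinks through death.

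Protocol 2.4 intends QoL data to help determine the relative benefits of the two treatments, so the population behind the 3-month contrast should be clear.

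**Working it through.** **1. The plan's own figure.** Inputs: 17% versus 34%, two-sided 5%, 80% power (protocol 14.3, SAP 1.2). The rates are 0.20 × 0.85 = 0.17 and 0.40 × 0.85 = 0.34.
- Pooled-variance formula: n = [1.960 × √(2 × 0.255 × 0.745) + 0.842 × √(0.17 × 0.83 + 0.34 × 0.66)]² / 0.17² = 102.003, so 103 per arm.
- Continuity correction: n/4 × [1 + √(1 + 4/(n × 0.17))]² = 113.5, so 114 per arm, or 228 in total. This matches the plan.

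The 15% therefore belongs to the pain-response calculation: "Assuming a 15% drop out/inevaluable rate". No sample size, SD or power is stated for QoL.

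**2. How many patients the t-test scores.** With missing share m for 3-month forms (assumed; 15% is a proxy only), the number scored is 228 × (1 − m). The difference detectable with 80% power is (1.960 + 0.842) × √(2/n per arm).

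| m | scored | not scored | detectable difference |
|---|---|---|---|
| 0% | 228 | 0 | 0.371 SD |
| 10% | 205 | 23 | 0.391 SD |
| 15% | 194 | 34 | 0.402 SD |
| 30% | 160 | 68 | 0.444 SD |

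At an assumed SD of 25, power for a 10-point difference (the relevance threshold in protocol 14.7) falls from 85.5% with no missing forms to 79.5% at 15%. The loss of precision is modest.

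**3. How many conflict with the stated set.** Of the 34 unscored at 15%, only those with a 4-week or 6-month form belong to the SAP 2.9.2 set. That is somewhere from 0 to 34 (17 if half have one). The documents do not give the split.

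**4. Within-arm bias.** If unscored patients average D points worse than scored patients, the completers' mean is too good by m × D. To put a scale on D, assume SD of change 25, correlation 0.6 between the 4-week and 3-month changes, and logistic drop-out on the 4-week change with log-odds 0.7 or 1.2 per SD.

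| m | bias, slope 0.7 | bias, slope 1.2 |
|---|---|---|
| 10% | 1.0 | 1.6 |
| 15% | 1.5 | 2.3 |
| 20% | 2.0 | 3.0 |
| 30% | 2.9 | 4.3 |

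At 15% this corresponds to D of about 10 (1.5/0.15) to 15 (2.3/0.15) points.

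**5. Bias in the arm difference.**
- Same drop-out mechanism in both arms, true arm difference of 8 to 10 points at 4 weeks, 15% missing overall: about 0.3 to 0.7 points.
- Same mechanism and no arm effect: zero.
- 10% versus 20% missing: 1.97 − 1.02 = 0.95 and 2.98 − 1.59 = 1.39 points. The SE is 25 × √(1/102.6 + 1/91.2) = 3.6, so the shift is 0.3 to 0.4 SE, in favour of the arm with more missing forms.

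**6. What a model would gain.** In simulation, a likelihood estimate using the 4-week score removed the arm bias when drop-out depended on that score. It roughly halved the bias when drop-out also depended on the unseen 3-month score. Separately, adjusting for baseline multiplies the SE of a change-score comparison by √((1 + ρ)/2), where ρ is the baseline-to-follow-up correlation and variances are equal. That is a reduction of 19% at ρ = 0.3 and 8% at ρ = 0.7 (assumed range).

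**The case against.** The strongest reply is that a comparison at one visit naturally uses patients with data at that visit, and that for a secondary endpoint this is simple and defensible. SAP 2.9.2 opens the whole QoL section, and its set fits the response analysis, which is the QoL analysis that protocol 14.7 names. The plan also limits and exposes missingness to a degree. There is a window of four weeks either side of 3 months. Protocol Appendix VI provides for completion at home, by mail or by telephone. Table 35 reports forms received by arm. Deaths appear in the 3-month survival estimates and Table 23. The likely distortion of the arm difference is small against the 10-point threshold, and every input behind it except the sample size is assumed. All of that stands, and it is why the priority is minor. It does not supply a missing-data rule, and none of those tables shows how deaths and missing forms together shape the scored 3-month group.

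Four stronger readings are tempting, and the documents do not support them:
- A reader might infer that the plan expects 15% to die or drop out before 3 months. The 15% is a combined allowance for pain response. Under protocol 10.1.1 it can include living patients with incomplete pain or opioid data.
- A reader might infer that everyone without a 3-month form is wrongly left out. Patients with no follow-up form at all are outside the SAP 2.9.2 set too.
- A reader might infer that the 4-week form is discarded. It is used in SAP 2.9.2.3 and 2.9.2.5, and is unused only in the primary QoL test.
- A reader might infer that any imbalance in drop-out biases the comparison. Drop-out must also relate to outcome, and no figure in the documents shows an imbalance.

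**Conclusion.** The point holds in limited form. The primary QoL test is complete-case and unadjusted, its population is narrower than the stated QoL set, and no rule covers missing scores or deaths.

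On the assumed 15% proxy, about 34 of 228 patients would be unscored (23 to 68 over 10% to 30%). The within-arm 3-month change would be roughly 1.5 to 2.3 points too favourable. The arm difference would be off by under 1 point with similar drop-out, and by about 1.0 to 1.4 points at 10% versus 20% missing. These sizes rest on the assumed SD, correlation and drop-out slopes. The text-based finding, that the set and the test do not match and that no rule exists, does not depend on them.

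This is not a flaw that invalidates the QoL comparison. It is a cheap improvement to a secondary endpoint, using data already scheduled.

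**What to change.** In SAP 2.9.2.4, make the primary QoL estimate the 3-month arm contrast from a repeated-measures mixed model. The outcome is change from baseline at 4 weeks, 3 months and 6 months. The terms are arm, visit, arm-by-visit, baseline score and baseline-by-visit, with unstructured covariance. The population is the set already defined in SAP 2.9.2. Keep the two-sample t-test as a sensitivity analysis and say that it uses only patients with a 3-month form.

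Beside the estimate, show by arm the deaths before 3 months and the missing 3-month forms with reasons, since the compliance denominator removes deaths. Add a simple missing-not-at-random analysis, for example making unobserved 3-month changes 5, 10 or 20 points worse, in both arms and then in one.

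The same edit should name the primary QoL domain, which SAP 2.9.2.4 leaves open. It should also settle how the t-test there relates to the Wilcoxon test of the same 3-month change in SAP 2.9.2.3.

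The cost is SAP wording and one standard model per score, with no new data. The downside is that the model assumes data missing at random and implicitly extrapolates scores past death. It reduces but does not remove bias if drop-out depends on unseen scores, which is why the death counts and the sensitivity analysis belong with it.

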### **2.9.2.5 QoL response analysis**

QOL response analysis is the CCTG QoL committee recommended analysis, and is calculated as follows: for a functional domain, a change score of 10 points from baseline was defined as clinically relevant. Patients were considered improved if reported a score 10-points or better than baseline at any time of QOL assessment. Conversely, patients were considered worsened if reported a score minus 10-points or worse than baseline at any time of QOL assessment without above defined 10-point improvement. Patients whose scores were between 10-point changes from baseline at every QOL assessment were considered as stable. In contrast to functional domains, for the determination of patient's QOL response, classification of patients into improved and worsened categories is reversed for symptom domains and single items. Chi-square and Mantel-Haenszel chi-square test for trend is used to test if there is a trend that patients in one treatment arm have higher proportions in the better QoL categories than those on the other arm. (Table 38).

